2.4.6. Feasibility Analysis

The feasibility analysis will be performed on the ITT population and PP population.

2.4.6.1. Primary Feasibility Analysis

The primary feasibility analysis is the proportion of subjects that achieve Acute Procedural Success (APS) defined as the percutaneous endocardial creation of a complete, electrically isolating set of lesions around the ostia of the pulmonary veins (PVI) using the FARAPULSE Endocardial Multi Ablation System during the Index Procedure, as clinically assessed by entrance and/or exit block performed \geq 20 minutes after the last PVI lesion is made.

CONFIDENTIEL / CONFIDENTIAL

Toute reproduction ou distribution, totale ou partielle, de ce document, sans autorisation préalable de ICON PLC est interdite.
Reproduction and distribution of this document, in whole or in part, is strictly forbidden without prior authorization from ICON PLC.

	STATISTICAL ANALYSIS PLAN	FARAPULSE PersAFOne SAP V1.0 PERSAFONE Page 17 /49
---	----------------------------------	--

2.4.6.2. Secondary Feasibility Analysis

The secondary feasibility analyses are:

- The proportion of subjects who undergo the protocol-specified 75-Day Remapping Procedure and achieve Chronic Procedural Success (CPS) defined as persistent electrical isolation of all initially ablated pulmonary veins. Chronic Procedural Success will be subdivided by Index Procedure only CPS and Reablated CPS subjects.
- The proportion of attempted subjects that achieve Acute CTI Success, defined as the creation of bi-directional electrical block across the CTI using the investigational devices.
- Durability of the CTI and/or other extra-PV lesion set(s), when applicable.
Durability is defined as unaltered integrity of each such lesion assessed at the Remapping Procedure.
- The proportion of subjects that achieve Therapeutic Success, defined as freedom from:
 - Post-Blanking Period through assessment: occurrence of AF, AFL or AT, or ablation for AF/AFL/AT using the study device
 - At any time: ablation for AF/AFL/AT with a non-study device
Therapeutic Success will be assessed from the end of the 90 Day Blanking Period through Months 6 and 12 and will be subdivided by on / off AADs (Atrial Fibrillation Drugs) post-Blanking Period.

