PRIMARY FEASIBILITY ENDPOINT:	The proportion of subjects that achieve Acute Procedural Success (APS) defined as the percutaneous endocardial creation of a complete, electrically isolating set of lesions around the ostia of the pulmonary veins (PVI) using the FARAPULSE Endocardial Multi Ablation System during the Index Procedure, as clinically assessed by entrance and/or exit block performed \geq 20 minutes after the last PVI lesion is made.

SECONDARY FEASIBILITY ENDPOINTS:	
1. The proportion of subjects who undergo the protocol-specified 75-Day Remapping Procedure and achieve Chronic Procedural Success (CPS) defined as persistent electrical isolation of all initially ablated pulmonary veins. Chronic Procedural Success will be subdivided by Index Procedure only CPS and Reablated CPS subjects.2. The proportion of attempted subjects that achieve Acute CTI Success, defined as the creation of bi-directional electrical block across the cavotricuspid isthmus using the investigational devices using the FARAPULSE Endocardial Multi Ablation System during the Index Procedure.3. Durability of the CTI and/or other extra-PV lesion set(s), when applicable. Durability is defined as unaltered integrity of each such lesion assessed at the Remapping Procedure.4. The proportion of subjects that achieve Therapeutic Success, defined as freedom from:
a. Post Blanking Period through assessment: occurrence of AF, AFL or AT or ablation for AF/AFL/AT using the study deviceb. At any time: ablation for AF/AFL/AT with a nonstudy device 
Therapeutic Success will be assessed from the end of the 90-day Blanking Period through Months 6 and 12 and will be subdivided by on / off AFDs (Atrial Fibrillation Drugs) post-Blanking Period.

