6.2 Secondary Safety Endpoints

1. The Primary Safety Endpoint assessed at 7 rather than 30 days
2. The proportion of subjects with a device- or procedure-related SAE
3. The proportion of subjects with stroke or TIA
4. The proportion of subjects requiring cardioversion
5. The proportion of subjects requiring an arrhythmia-related hospitalization

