2.4.8.2. Secondary Safety Analysis

The proportion of subjects reporting one or more SAEs for each follow-up interval. The intervals will include the period from:

- The Primary Safety Endpoint assessed at 7 rather than 30 days
- The proportion of subjects with a device- or procedure-related SAE
- The proportion of subjects with stroke or TIA
- The proportion of subjects requiring cardioversion
- The proportion of subjects requiring an arrhythmia-related hospitalization.

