- Derived criteria "Durability of Left atrial roof line at remap" will be defined as follows:
IF Left atrial roof line lesion durable ='Yes' in **Follow-up 3D electroanatomical mapping form (RM)** **THEN** Durability of Left atrial roof line at remap = 'Yes'
ELSE IF Left atrial roof line lesion durable ='No' in **Follow-up 3D electroanatomical mapping form (RM)** **THEN** Durability of Left atrial roof line at remap = 'No'
- Derived criteria "Durability of Left atrial Posterior line" will be defined as follows:
IF Left atrial Posterior line lesion durable ='Yes' in **Follow-up 3D electroanatomical mapping form (RM)** **THEN** Durability of Left atrial Posterior line at remap = 'Yes'
ELSE IF Left atrial Posterior line lesion durable ='No' in **Follow-up 3D electroanatomical mapping form (RM)** **THEN** Durability of Left atrial Posterior line at remap = 'No'
- Derived criteria "Therapeutic Success ON/OFF AAD" will be defined as follows:

CONFIDENTIEL / CONFIDENTIAL

Toute reproduction ou distribution, totale ou partielle, de ce document, sans autorisation préalable de ICON PLC est interdite.
Reproduction and distribution of this document, in whole or in part, is strictly forbidden without prior authorization from ICON PLC.

IF "AF/AFL/AT status"= 0 **AND** "RF touchup"= 0 **AND** "ABL >90 days" = 0 **in MDT excel file**
THEN therapeutic success='Yes'
ELSE therapeutic success='No'

- Derived criteria "Therapeutic Success Off ADD" will be defined as follows:
IF Therapeutic success ='Yes' **AND** Class I/III AAD>90days=0 **in MDT excel file** **THEN** therapeutic success Off ADD ='YES'
ELSE IF Therapeutic success ='No' **AND** Class I/III AAD>90days=0 **in MDT excel file** **THEN** **THEN** therapeutic success Off ADD ='NO'
- Derived criteria "Therapeutic Success On ADD" will be defined as follows:
IF Therapeutic success ='Yes' **AND** Class I/III AAD>90days=1 **in MDT excel file** **THEN** therapeutic success On ADD ='No'
Else If Therapeutic success ='No' **AND** Class I/III AAD>90days=1 **in MDT excel file** **THEN** **THEN** therapeutic success On ADD ='No'

Additional endpoints

- Derived criteria "Proportion of all ablated pulmonary veins that are isolated at the Index Procedure using the study device" will be defined as follows:

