4.1.12. Table 12. Secondary Safety Endpoints

	ITT Population N = XX	
	n/N (%)	[95% CI]
Primary Safety Endpoint (Early and Late Onset Composite Safety Endpoint) assessed at 7 days	XX/XX (XX.X%)	[XX% - XX%]
Total Early (within 30 days of Index or Remap Procedure)	XX/XX (XX.X%)	[XX% - XX%]
Death	XX/XX (XX.X%)	[XX% - XX%]
Myocardial infarction (MI)	XX/XX (XX.X%)	[XX% - XX%]
Persistent diaphragmatic paralysis	XX/XX (XX.X%)	[XX% - XX%]
Stroke	XX/XX (XX.X%)	[XX% - XX%]
Transient ischemic attack (TIA)	XX/XX (XX.X%)	[XX% - XX%]
Peripheral or organ thromboembolism	XX/XX (XX.X%)	[XX% - XX%]
Pericarditis	XX/XX (XX.X%)	[XX% - XX%]
Cardiac tamponade / perforation	XX/XX (XX.X%)	[XX% - XX%]
Vascular access complications requiring intervention	XX/XX (XX.X%)	[XX% - XX%]
Heart block	XX/XX (XX.X%)	[XX% - XX%]
Total Late (any time during follow-up through 12 months)	XX/XX (XX.X%)	[XX% - XX%]

CONFIDENTIEL / CONFIDENTIAL

Toute reproduction ou distribution, totale ou partielle, de ce document, sans autorisation préalable de ICON PLC est interdite.
Reproduction and distribution of this document, in whole or in part, is strictly forbidden without prior authorization from ICON PLC.

ICON	STATISTICAL ANALYSIS PLAN	FARAPULSE PersAFOne SAP V1.0 PERSAFONE Page 43 /49
-------------	----------------------------------	--

Pulmonary vein (PV) stenosis (> 70% diameter reduction from baseline)	XX/XX (XX.X%)	[XX% - XX%]
Atrio-esophageal fistula	XX/XX (XX.X%)	[XX% - XX%]
Device-Related Serious Adverse Events (SAEs)	XX/XX (XX.X%)	[XX% - XX%]
Procedure-Related Serious Adverse Events (SAEs)	XX/XX (XX.X%)	[XX% - XX%]
Stroke	XX/XX (XX.X%)	[XX% - XX%]
Transient Ischemic Attack (TIA)	XX/XX (XX.X%)	[XX% - XX%]
Cardioversion	XX/XX (XX.X%)	[XX% - XX%]
Arrhythmia-related (AF, AFL, AT) hospitalization	XX/XX (XX.X%)	[XX% - XX%]

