4.1.13. Table 13. Secondary Feasibility Endpoints

	ITT Population	
	N = XX	[95% CI]
Chronic Procedural Success (CPS)* for subjects who undergo the protocol-specified 75-Day Remapping Procedure	XX/XX (XX.X%)	[XX% - XX%]
Acute Cavotricuspid isthmus (CTI) Success**	XX/XX (XX.X%)	[XX% - XX%]
Therapeutic Success***	XX/XX (XX.X%)	[XX% - XX%]
On AADs	XX/XX (XX.X%)	[XX% - XX%]
Off AADs	XX/XX (XX.X%)	[XX% - XX%]
Durability of the CTI and/or other extra PV lesion set(s)	XX/XX (XX.X%)	[XX% - XX%]

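### SAP 2.5 and Tables 12 and 13 do not carry through three defined secondary results: 6-month Therapeutic Success, device- or procedure-related SAE, and stroke or TIA

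*SAP*

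**What the plan says.** **Therapeutic Success.** The Protocol's Executive Summary says "Therapeutic Success will be assessed from the end of the 90-day Blanking Period through Months 6 and 12", and Protocol 6.4 says the same. SAP 2.4.6.2 repeats it: "Therapeutic Success will be assessed from the end of the 90 Day Blanking Period through Months 6 and 12", split by drug use after blanking. SAP 2.5 then defines success from three indicators in the sponsor-supplied MDT file: "IF 'AF/AFL/AT status'= 0 AND 'RF touchup'= 0 AND 'ABL >90 days' = 0". None of the three has a time limit. In Table 13 the row "Therapeutic Success" appears once, with On AADs and Off AADs beneath it and no time point.

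**Device- or procedure-related SAE.** SAP 2.4.8.2, like Protocol 6.2, asks for "The proportion of subjects with a device- or procedure-related SAE". SAP 2.5 derives a device-related flag and a procedure-related flag, and Table 12 prints one row for each.

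**Stroke or TIA.** Protocol 6.2 asks for "The proportion of subjects with stroke or TIA", and SAP 2.4.8.2 repeats it. SAP 2.5 derives stroke alone and TIA alone, each after the index procedure and again after the remap. Table 12 prints a stroke row and a TIA row.

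**The concern.** In each case the endpoint is defined clearly in words, but the programming rule and the table shell produce something else. A programmer works from the derivations and shells.

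For Therapeutic Success, a subject whose first failure falls at month 10 is a failure in the only row printed. That subject's success at 6 months appears nowhere in the table.

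For the two safety endpoints, the components can overlap. One SAE may be related to both device and procedure, and one subject may have both a stroke and a TIA. The printed rows therefore do not determine the proportion that the protocol defines.

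If the gap is left until the data are known, the cut day, the drug-status rule and the combination rule would be settled after the results have been seen.

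**Working it through.** The plan gives no figure to reproduce. The study is descriptive, with no hypothesis test and no required sample size (Protocol 5.3, SAP 2.2). The check traces each endpoint from definition to derivation to table, then illustrates the size of the gap with assumed counts and rates.

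**Trace**

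| Endpoint | Definition | SAP 2.5 | Table |
|---|---|---|---|
| Therapeutic Success | Months 6 and 12 (Protocol 6.4, SAP 2.4.6.2) | one undated flag | Table 13: one row plus on/off drug |
| Device- or procedure-related SAE | one subject proportion (Protocol 6.2, SAP 2.4.8.2) | two separate flags | Table 12: two rows |
| Stroke or TIA | one subject proportion (same sections) | separate flags, after index and after remap | Table 12: two rows |

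**Is the 6-month result produced elsewhere?**
- Table 7 is a 12-month table. Its only 6-month row is Holter compliance.
- SAP 2.1.4 gives Kaplan-Meier rates at 180 and 365 days, but Graphs 2 to 10 plot other outcomes. Graphs 2 to 5 are freedom from AF/AFL/AT or from AF, split by drug. Graphs 6 to 10 also require no cardioversion after day 90, which is not part of Therapeutic Success.
- Time to Therapeutic Failure has no rule in SAP 2.5 and no graph. Table 11 lays it out as mean, SD, median and quartiles.
- The MDT file (SAP 2.3, Databases) lists time variables only for AF and for AF/AFL/AT. RF touch-up and ablation after day 90 are indicators without a listed date.

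**Are the either/or endpoints produced elsewhere?** The early composite in SAP 2.5 joins TIA with CVA, but together with other events and within its own window. No rule joins stroke with TIA over follow-up, or device-related with procedure-related SAE.

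**Size of the either/or gap.** If *a* subjects are in one row and *b* in the other, the number in at least one row lies between max(*a*, *b*) and min(*N*, *a* + *b*). Take assumed counts *a* = 2 and *b* = 3, so the range is 3 to 5 subjects. Intervals are exact (Clopper-Pearson) 95%.
- *N* = 40 (planned maximum, Protocol 3.7): 3/40 = 7.5% (1.6% to 20.4%) up to 5/40 = 12.5% (4.2% to 26.8%).
- *N* = 25 (the value in the shells of Tables 5 and 19): 3/25 = 12.0% (2.5% to 31.2%) up to 5/25 = 20.0% (6.8% to 40.7%).

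With one stroke subject and one TIA subject, the endpoint is 1 or 2 subjects: 2.5% or 5.0% at 40, and 4.0% or 8.0% at 25. If either row is zero, the endpoint equals the other row and nothing is lost.

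**Size of the 6- versus 12-month gap.** Assume a constant failure hazard from day 90. At days 180 and 365 the times at risk are 90 and 275 days, so S6 = S12^(90/275). At the upper visit windows, 180 + 30 = 210 and 365 + 30 = 395, they are 120 and 305 days, so S6 = S12^(120/305).

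| Assumed 12-month success | 6-month, days 180/365 | 6-month, days 210/395 |
|---|---|---|
| 50% | 79.7% | 76.1% |
| 60% | 84.6% | 81.8% |
| 70% | 89.0% | 86.9% |
| 80% | 93.0% | 91.6% |

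Under this assumption one undated row cannot stand for both times.

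**A defect in the same derivation.** The SAP 2.5 rule for success on drug assigns No when Therapeutic Success is Yes and also when it is No. As written, the On AADs row would show 0% whatever the data.

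**The case against.** A reader might infer that three secondary endpoints will go unreported. The documents do not support that. SAP 2.4.6.2 and 2.4.8.2 commit to all three in the protocol's terms, and the single Therapeutic Success row can serve as the 12-month result. The fault is that derivations and shells lag behind the text.

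Nor can one say that a 6-month figure could never be produced:
- The 180-day rule in SAP 2.1.4 applies to time-to-event variables, and Time to Therapeutic Failure is a listed endpoint.
- SAP 2.4.5 describes follow-up at 6 and 12 months.
- The Databases section says the sponsor's file will keep one structure for each analysis, so the same rule could be run on a file frozen at 6 months.
- The asterisked note to the Table 13 row is absent from the text available, so it may have named a time point.

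These points soften the conclusion but do not remove it. No table or graph applies the 180-day rule to Therapeutic Failure, and the SAP does not say that a 6-month run is planned.

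On the safety pairs, Listings 14, 16 and 17 may let a reader count the combined subjects by hand. The event summaries in Protocol 1.3.1 and 1.3.2 mention no stroke or TIA among 40 + 60 = 100 enrolled subjects, so the practical effect on that pair may be nil. That readers would add the overlapping rows is conjecture. It remains true that the defined proportion has no rule and no row.

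**Conclusion.** The point holds as a specification gap worth closing before analysis. The 6-month Therapeutic Success result is not tabulated, and two safety endpoints appear only as components that bound them.

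The 5-point range at 40 subjects and the 8-point range at 25 are illustrations. They rest on the assumed counts of 2 and 3 and on maximum uncertainty about overlap. The 6-month success rates rest on assumed 12-month rates and a constant hazard. The trace itself needs no assumption.

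The consequence is confined to descriptive secondary endpoints. Neither primary endpoint nor the sample size is touched.

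**What to change.** **(a) Therapeutic Success.** In SAP 2.5, derive it twice, counting failures dated up to the upper visit windows that SAP 2.1.4 already uses (days 210 and 395).
- Take recurrence dates from the AF/AFL/AT km days in the MDT file. The SAP should state that this is the day of first recurrence when the status is 1.
- Take ablation dates from the e-CRF, assuming they are recorded there. State which source prevails if it disagrees with the MDT indicators.
- Keep ablation with a non-study device as a failure at any time up to the cut, including during blanking.
- Show a 6-month and a 12-month column in Table 13.
- State how on/off-drug status is assigned at each time from the recorded medication data, or say that the existing post-blanking flag serves for both.
- Correct the on-drug rule so that a success on drug returns Yes.

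**(b) Safety endpoints.** Add to SAP 2.5 two per-subject flags, any device- or procedure-related SAE and any stroke or TIA. Make them the endpoint rows of Table 12 and keep the present rows as components.

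**Cost.** SAP wording, two dated flags, two either/or flags, one table column, two table rows and one corrected rule. There is some programming to link e-CRF ablation dates to the MDT file, and more if drug status is made time-specific. No new assessments are needed.

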2.4.7. Additional endpoints

The additional observations will be performed on the ITT population and will include:

- Proportion of subjects with early recurrence of atrial fibrillation (ERAF) by 90 days after the initial study ablation.
- Time to Therapeutic Failure
- Proportion of all ablated pulmonary veins that are isolated at the Index Procedure using the study device.
- Proportion of all ablated pulmonary veins isolated using the study device during the Index Procedure that remain isolated at the 75-day Remapping Procedure.
- The proportion of attempted subjects that achieve Chronic CTI Success, defined as persistent bi-directional electrical block across the CTI as assessed at the 75-day remapping procedure.
- The proportion of attempted subjects that achieve Chronic Focal Success, defined as persistent electrical nonconductivity of extra-PV tissue targeted for ablation in the Index Procedure, excluding the CTI

2.4.8. Safety Endpoint

Descriptive statistical data is used to analyze the Primary Safety Endpoint (PSE), the secondary safety endpoints and others analysis. The analysis is performed on the ITT populations.

The Safety endpoint will be performed on the ITT population and will include

2.4.8.1. Primary Safety Analysis

The primary safety endpoint for this study is the Composite Safety Endpoint (CSE) defined as the incidence of the following early-onset and late-onset serious adverse events (SAEs) which are device- or procedure-related, as adjudicated by the CEDMC.

CONFIDENTIEL / CONFIDENTIAL

Toute reproduction ou distribution, totale ou partielle, de ce document, sans autorisation préalable de ICON PLC est interdite.
Reproduction and distribution of this document, in whole or in part, is strictly forbidden without prior authorization from ICON PLC.

STATISTICAL ANALYSIS PLAN

FARAPULSE PersAFOne SAP V1.0

PERSAFONE

Page 18 /49

Composite Safety Endpoint Definitions:

Early onset (within 30 days of an Index or Remap Procedure)

- Death
- Myocardial infarction (MI)
- Persistent diaphragmatic paralysis
- Stroke or transient ischemic attack (TIA)
- Peripheral or organ thromboembolism
- Pericarditis
- Cardiac tamponade / perforation
- Vascular access complications requiring intervention
- Heart block

Late onset (any time during follow-up through 12 months):

- Pulmonary vein (PV) stenosis (> 70% diameter reduction from baseline)
- Atrio-esophageal fistula

2.4.8.2. Secondary Safety Analysis

The proportion of subjects reporting one or more SAEs for each follow-up interval. The intervals will include the period from:

- The Primary Safety Endpoint assessed at 7 rather than 30 days
- The proportion of subjects with a device- or procedure-related SAE
- The proportion of subjects with stroke or TIA
- The proportion of subjects requiring cardioversion
- The proportion of subjects requiring an arrhythmia-related hospitalization.

2.4.8.3. Other Safety and Tolerance Analysis

Descriptive statistics is used to draw up a recapitulation of adverse event. The following data is presented on the ITT population. All AEs are reported by the System organ class (SOC) and the preferred term (PT) (according to coding MedDRA) as follows:

- Total number of Adverse Event (AE) (not including SAEs) reported, number and percentage of subjects with at least one AE reported
- Total number of Serious Adverse Event (SAE) reported, number and percentage of subjects with at least one SAE reported
- Total number of Deaths
- Total number of Device deficiency (DD) reported, number and percentage of subjects with at least one DD reported

2.4.9. Concomitant Medications

Concomitant medications will be listed on the ITT population.

CONFIDENTIEL / CONFIDENTIAL

Toute reproduction ou distribution, totale ou partielle, de ce document, sans autorisation préalable de ICON PLC est interdite.
Reproduction and distribution of this document, in whole or in part, is strictly forbidden without prior authorization from ICON PLC.

	STATISTICAL ANALYSIS PLAN	FARAPULSE PersAFOne SAP V1.0 PERSAFONE Page 19 /49
---	----------------------------------	--

2.5. Derived Criteria Calculation

If at least one of the items needed to calculate a derived criteria is missing, then the corresponding derived criteria will be considered as missing.

Patient Disposition:

- Derived criteria “Enrolled population” will be analysed as:
IF the date of patient consent is filled in **Patient eligibility form (IE)** **THEN** “Enrolled population” = ‘Yes’
ELSE “Enrolled population” = ‘No’.
- Derived criteria “ITT population” will be defined as follows:
IF “Enrolled population” = ‘Yes’ in **Patient eligibility form (IE)** and the date of the Procedure is filled in **Procedural data form (PR)** **THEN** “ITT population” = ‘Yes’
ELSE “ITT population” = ‘No’.
- Derived criteria “Per Protocol population PP” will be defined as follows:
IF “ITT population” = ‘Yes’ **AND** Device Deficiency Number is not filled **AND** Serial # is not filled in **Device Deficiency DD Form** **THEN** Per Protocol population = ‘Yes’
ELSE Per Protocol population = ‘No’.
- Derived criteria “Time of patient follow-up” will be calculated as:
Date of study exit/withdrawal (*) in **Patient eligibility form (IE)** – date of procedure in **Procedural data form (PR)**
*if the patient is still in the study, the last visit date will be used instead of the exit/ withdrawal one.
- Derived criteria “COVID status” will be calculated as:
IF “Related to COVID-19 situation” =1 **OR** the term “COVID” exist in “reason for deviation” **AND** date of deviation is filled in **Protocol deviation form (PD)**, **THEN** CLASS=“ COVID-19”
ELSE IF date of deviation is filled **THEN** CLASS= “NOT COVID-19”.

Baseline Patient Characteristics:

- Derived criteria “Time from first AF diagnosis until consent date (months)” will be defined as follows:
Informed consent date – date of first documented AF diagnosis in **AF history form (AH)**.
- Derived criteria “Time between the most recent AF episode and the enrollment (months)” will be defined as follows:
Informed consent date – date of most recent AF episode in **AF history form (AH)**.
- Derived criteria “Permanent pacemaker or ICD” will be defined as follows:
IF Pacemaker, Implantable Cardioverter Defibrillator or Cardiac Resynchronization therapy device= ‘Yes’ in **Patient eligibility Form (IE)** **THEN** Permanent pacemaker or ICD=‘Yes’

CONFIDENTIEL / CONFIDENTIAL

Toute reproduction ou distribution, totale ou partielle, de ce document, sans autorisation préalable de ICON PLC est interdite.
Reproduction and distribution of this document, in whole or in part, is strictly forbidden without prior authorization from ICON PLC.

	STATISTICAL ANALYSIS PLAN	FARAPULSE PersAFOne SAP V1.0 PERSAFONE Page 20 /49
---	----------------------------------	--

ELSE IF Pacemaker, Implantable Cardioverter Defibrillator or Cardiac Resynchronization therapy device ='No' in **Patient eligibility Form (IE)** **THEN** Permanent pacemaker or ICD='No'

Index Procedure:

- Derived criteria "Procedure time (hours)" will be defined as follows:
Procedure end- Procedure start in **Procedural data form (PR)**.
- Derived criteria "FARAWAVE dwell time (hours)" will be defined as follows:
SUM of [(FARAWAVE ablation catheter remove 1 – FARAWAVE ablation catheter introduction 1), (FARAWAVE ablation catheter remove n – FARAWAVE ablation catheter introduction n)] in **Procedural data form (PR)**
- Derived criteria "PVI ablation time (hours)" will be defined as follows:
Last PVI ablation time - First PVI ablation time in **Procedural data form (AB)**
- Derived criteria "CTI (FARAFLEX) dwell time (hours)" will be defined as follows:
SUM of [(FARAFLEX ablation catheter remove 1 – FARAFLEX ablation catheter introduction 1), (FARAFLEX ablation catheter remove n – FARAFLEX ablation catheter introduction n)] in **Procedural data form (PR)**
- Derived criteria "LAPW ablation time (hours)" will be defined as follows:
Last LAPW ablation time - First LAPW ablation time in **Procedural data form (AB)**
- Derived criteria "Total number of PVI applications" will be defined as follows:
SUM of [(Count (Ablation location **IN** ("Left superior", "Left inferior", "Right superior", "Right inferior", "Right middle", "Left common ostium") **OR** (Ablation location='Other' **AND** Ablation location, Other specify='LCPV')))] in **Procedural data form (AB)**
- Derived criteria "Number of LAPW applications" will be defined as follows:
SUM of [(Count (Ablation location='Other' **AND** Ablation location, Other specify **IN** ("LA PW", "LAPW", "LEFT ATRIAL POSTERIOR WALL")))] in **Procedural data form (AB)**
- Derived criteria "Total number of CTI applications" will be defined as follows:
SUM of [(Count (Ablation location=" CTI"))] in **Procedural data form (AB)**
- Derived criteria "Total number of veins treated" will be defined as follows:
COUNT of ["left superior", "left inferior", "left common ostium", "right middle", "right superior", "right inferior"] **WHERE** isolated/Blocked in ('Yes', 'No') in **Procedural data form (PR)**
- Derived criteria "Total number of veins isolated" will be defined as follows:
SUM of [left superior, left inferior, left common ostium, right middle, right superior, right inferior] **WHERE** isolated/Blocked = 'Yes' in **Procedural data form (PR)**

CONFIDENTIEL / CONFIDENTIAL

Toute reproduction ou distribution, totale ou partielle, de ce document, sans autorisation préalable de ICON PLC est interdite.
Reproduction and distribution of this document, in whole or in part, is strictly forbidden without prior authorization from ICON PLC.

	STATISTICAL ANALYSIS PLAN	FARAPULSE PersAFOne SAP V1.0 PERSAFONE Page 21 /49
---	----------------------------------	--

- Derived criteria "Of the total number of veins treated, the number of veins isolated (Proportion of veins isolated)" will be defined as follows:
Derived criteria "Total number of veins isolated"/ Derived criteria "Total number of veins treated"
- Derived criteria Proportion "CTI acute isolation" will be defined as follows:
COUNT of [CTI isolated/Blocked='Yes' /CTI Attempted='Yes'] in **Procedural data form (PR)**

Remapping at 75 Days

- Derived criteria "Days follow up at remap" will be defined as follows:
Remapping date – Date of index procedure
- Derived criteria "Durable PVI" will be defined as follows:
IF Left Superior Lesion durable='Yes' **AND** Left Inferior Lesion durable='Yes' **AND** Left Common Ostium Lesion durable='Yes' **AND** Right Middle Lesion durable='Yes' **AND** Right Superior Lesion durable='Yes' **AND** Right Inferior Lesion durable='Yes' **AND** CTI Lesion durable='Yes' **AND** Mitral Isthmus Lesion durable='Yes' **AND** Left Atrial Roof Line Lesion durable='Yes' **AND** Left Atrial Posterior Line Lesion durable='Yes' **AND** Other 1 Lesion durable='Yes' in **Follow-up 3D electroanatomical mapping form (RM)** **THEN** Durable PVI='Yes'
ELSE Durable PVI='No'
- Derived criteria "LAPW chronic isolation" will be defined as follows:
IF Anatomical Structure/Area other specification 1 **IN** ("POSTERIOR WALL" "LA POSTERIOR WALL" "LAPW" "PA WALL" "BOX POSTERIOR WALL") **AND** Other 1 Lesion durable = 'yes' **OR** Anatomical Structure/Area other specification 2 **IN** ("POSTERIOR WALL" "LA POSTERIOR WALL" "LAPW" "PA WALL" "BOX POSTERIOR WALL") **AND** Other 2 Lesion durable = 'Yes' in **Follow-up 3D electroanatomical mapping form (RM)** **THEN** LAPW chronic isolation= 'Yes'
ELSE LAPW chronic isolation = 'No'
- Derived criteria "Number of veins durably isolated" will be defined as follows:
SUM of [LSPV chronic isolation='Yes', LIPV chronic isolation='Yes', LCPV chronic isolation='Yes', RSPV chronic isolation='Yes', RIPV chronic isolation='Yes', RMPV chronic isolation ='Yes'] in **Follow-up 3D electroanatomical mapping form (RM)**
- Derived criteria "Number of veins with gaps" will be defined as follows:
SUM of [LSPV chronic isolation='No', LIPV chronic isolation=' No', LCPV chronic isolation=' No', RSPV chronic isolation=' No', RIPV chronic isolation=' No', RMPV Chronic isolation = 'No'] in **Follow-up 3D electroanatomical mapping form (RM)**

6 and 12 Months follow up

- Derived criteria "TTM compliance (%) (calculated)" will be defined as follows:
(TTM weeks received /TTM weeks expected) *100 in **MDT excel file**
- Derived criteria "Holter compliance (%) at 6 months" will be defined as follows:

CONFIDENTIEL / CONFIDENTIAL

Toute reproduction ou distribution, totale ou partielle, de ce document, sans autorisation préalable de ICON PLC est interdite.
Reproduction and distribution of this document, in whole or in part, is strictly forbidden without prior authorization from ICON PLC.

	STATISTICAL ANALYSIS PLAN	FARAPULSE PersAFOne SAP V1.0 PERSAFONE Page 22 /49
---	----------------------------------	--

IF 6mo Holter in ('AF', 'none', 'SVT') in **MDT excel file** **THEN** Holter compliance (%) at 6 months = 'Yes'

ELSE IF 6mo Holter in ('MISSING') in **MDT excel file** **THEN** Holter compliance (%) at 6 months='No'

- Derived criteria "Holter compliance (%) at 12 months" will be defined as follows:

IF 12mo Holter in ('AF', 'none', 'SVT') in **MDT excel file** **THEN** Holter compliance (%) at 12 months = 'Yes'

ELSE IF 12mo Holter in ('MISSING') in **MDT excel file** **THEN** Holter compliance (%) at 12 months='No'

- Derived criteria "Freedom from AF/AFL/AT" will be defined as follows:

IF AF/AFL/AT status =0 in **MDT excel file** **THEN** Freedom from AF/AFL/AT ='Yes'

ELSE Freedom from AF/AFL/AT ='No'

- Derived criteria "Freedom from AF/AFL/AT with Class I/III AAD >90 days" will be defined as follows:

IF AF/AFL/AT status =0 **AND** Class I/III AAD >90 days =1 in **MDT excel file** **THEN** Freedom from AF/AFL/AT with Class I/III AAD >90 days ='Yes'

ELSE Freedom from AF/AFL/AT with Class I/III AAD >90 days ='No'

- Derived criteria "Freedom from AF/AFL/AT without Class I/III AAD >90 days" will be defined as follows:

IF AF/AFL/AT status =0 **AND** Class I/III AAD >90 days =0 in **MDT excel file** **THEN** Freedom from AF/AFL/AT without Class I/III AAD >90 days ='Yes'

ELSE Freedom from AF/AFL/AT without Class I/III AAD >90 days ='No'

- Derived criteria "Freedom from AF" will be defined as follows:

IF AF status =0 in **MDT excel file** **THEN** Freedom from AF ='Yes'

ELSE Freedom from AF ='No'

- Derived criteria "Freedom from AF with Class I/III AAD >90 days" will be defined as follows:

IF AF status =0 **AND** Class I/III AAD >90 days =1 in **MDT excel file** **THEN** Freedom from AF with Class I/III AAD >90 days ='Yes'

ELSE Freedom from AF with Class I/III AAD >90 days ='No'

- Derived criteria "Freedom from AF without Class I/III AAD >90 days" will be defined as follows:

IF AF status =0 **AND** Class I/III AAD >90 days =0 in **MDT excel file** **THEN** Freedom from AF without Class I/III AAD >90 days ='Yes'

ELSE Freedom from AF without Class I/III AAD >90 days ='No'

- Derived criteria "Freedom from AF/AFL/AT, no DCCV>90 days, no RF, no ablation >90 days" will be defined as follows:

CONFIDENTIEL / CONFIDENTIAL

Toute reproduction ou distribution, totale ou partielle, de ce document, sans autorisation préalable de ICON PLC est interdite.
Reproduction and distribution of this document, in whole or in part, is strictly forbidden without prior authorization from ICON PLC.

	STATISTICAL ANALYSIS PLAN	FARAPULSE PersAFOne SAP V1.0 PERSAFONE Page 23 /49
---	----------------------------------	--

IF AF/AFL/AT status =0 **AND** DCCV90D=0 **AND** RF touch up=0 **AND** ABL>90 day=0 in **MDT excel file** **THEN** Freedom from AF/AFL/AT, no DCCV>90 days, no RF, no ablation >90 days ='Yes'

ELSE Freedom from AF/AFL/AT, no DCCV>90 days, no RF, no ablation >90 days ='No'

- Derived criteria "Freedom from AF/AFL/AT, no DCCV>90 days, no RF, no ablation >90 days with Class I/III AAD >90 days" will be defined as follows:
IF AF/AFL/AT status =0 **AND** DCCV90D=0 **AND** RF touch up=0 **AND** ABL>90 day=0 **AND** Class I/III AAD >90 days =1 in **MDT excel file** **THEN** Freedom from AF/AFL/AT, no DCCV>90 days, no RF, no ablation >90 days with Class I/III AAD >90 days='Yes'
ELSE Freedom from AF/AFL/AT, no DCCV>90 days, no RF, no ablation >90 days with Class I/III AAD >90 days='No'
- Derived criteria "Freedom from AF/AFL/AT, no DCCV>90 days, no RF, no ablation >90 days without Class I/III AAD >90 days" will be defined as follows:
IF AF/AFL/AT status =0 **AND** DCCV90D=0 **AND** RF touch up=0 **AND** ABL>90 day=0 **AND** Class I/III AAD >90 days =0 in **MDT excel file** **THEN** Freedom from AF/AFL/AT, no DCCV>90 days, no RF, no ablation >90 days without Class I/III AAD >90 days= 'Yes'
ELSE Freedom from AF/AFL/AT, no DCCV>90 days, no RF, no ablation >90 days without Class I/III AAD >90 days='No'
- Derived criteria "Freedom from AF, no DCCV>90 days, no RF, no ablation >90 days" will be defined as follows:
IF AF status =0 **AND** DCCV90D=0 **AND** RF touch up=0 **AND** ABL>90 day=0 in **MDT excel file** **THEN** Freedom from AF, no DCCV>90 days, no RF, no ablation >90 days ='Yes'
ELSE Freedom from AF, no DCCV>90 days, no RF, no ablation >90 days ='No'
- Derived criteria "Freedom from AF, no DCCV>90 days, no RF, no ablation >90 days with Class I/III AAD >90 days" will be defined as follows:
IF AF status =0 **AND** DCCV90D=0 **AND** RF touch up=0 **AND** ABL>90 day=0 **AND** Class I/III AAD >90 days =1 in **MDT excel file** **THEN** Freedom from AF, no DCCV>90 days, no RF, no ablation >90 days with Class I/III AAD >90 days ='Yes'
ELSE Freedom from AF, no DCCV>90 days, no RF, no ablation >90 days with Class I/III AAD >90 days ='No'
- Derived criteria "Freedom from AF, no DCCV>90 days, no RF, no ablation >90 days without Class I/III AAD >90 days" will be defined as follows:
IF AF status =0 **AND** DCCV90D=0 **AND** RF touch up=0 **AND** ABL>90 day=0 **AND** Class I/III AAD >90 days =0 in **MDT excel file** **THEN** Freedom from AF/AFL/AT, no DCCV>90 days, no RF, no ablation >90 days without Class I/III AAD >90 days='Yes'
ELSE Freedom from AF/AFL/AT, no DCCV>90 days, no RF, no ablation >90 days without Class I/III AAD >90 days= 'No'

Primary feasibility endpoint

IF Ablation with study device was successful = 'Yes' in **procedural form (PR)** **THEN** APS='Yes'

CONFIDENTIEL / CONFIDENTIAL

Toute reproduction ou distribution, totale ou partielle, de ce document, sans autorisation préalable de ICON PLC est interdite.
Reproduction and distribution of this document, in whole or in part, is strictly forbidden without prior authorization from ICON PLC.

	STATISTICAL ANALYSIS PLAN	FARAPULSE PersAFOne SAP V1.0 PERSAFONE Page 24 /49
---	----------------------------------	--

ELSE IF Ablation with study device was successful = 'No' in **procedural form (PR)** **THEN**
APS='No'

Secondary Feasibility Analysis

- Derived criteria "Chronic Procedural Success (CPS)" will be defined as follows:
IF Has all ablation with the study device(s) been successful? ='Yes' in **Procedural data form (PR)** **AND** Has all ablation with the study device remain successful? ='Yes' **AND** Additional ablation(s) performed? ='No' in **FOLLOW UP 3D ELECTRO ANATOMICAL MAPPING form (RM)** **THEN** Chronic Procedural Success (CPS) ='Yes, index procedure only'
ELSE IF Has all ablation with the study device(s) been successful? ='Yes' in **Procedural data form (PR)** **AND** Has all ablation with the study device remain successful? ='No' **AND** Any PV reconnections noted? in = 'Yes' **AND** Additional ablation(s) performed? ='Yes' in **FOLLOW UP 3D ELECTRO ANATOMICAL MAPPING form (RM)** **THEN** Chronic Procedural Success (CPS) ='Yes, reblated'
ELSE IF Has all ablation with the study device(s) been successful? ='No' in **Procedural data form (PR)** **THEN** Chronic Procedural Success (CPS) ='No'
- Derived criteria Proportion "Acute Cavotricuspid isthmus (CTI) Success" will be defined as follows:
COUNT IF [CTI isolated/Blocked='Yes' AND CTI Attempted='Yes'] in **Procedural data form (PR)**
- Derived criteria "Durability of CTI at remap," will be defined as follows:
IF CTI lesion durable ='Yes' in **Follow-up 3D electroanatomical mapping form (RM)** **THEN** Durability of CTI at remap = 'Yes'
ELSE IF CTI lesion durable ='No' in **Follow-up 3D electroanatomical mapping form (RM)** **THEN** Durability of CTI at remap = 'No'
- Derived criteria "Durability of Mitral isthmus at remap" will be defined as follows:
IF Mitral isthmus lesion durable ='Yes' in **Follow-up 3D electroanatomical mapping form (RM)** **THEN** Durability of Mitral isthmus at remap = 'Yes'
ELSE IF Mitral isthmus lesion durable ='No' in **Follow-up 3D electroanatomical mapping form (RM)** **THEN** Durability of Mitral isthmus at remap = 'No'
